13.1 Electronic and central data validation

A designated person will supervise data collection and entry on a regular basis. The data manager will support onsite data entry teams. This process will be defined in the Data Management SOP.

13.2 On-site monitoring

13.2.1 Framework for monitoring

The study will be conducted in accordance with the current approved protocol, ICH GCP, relevant regulations and standard operating procedures. A monitoring plan will be finalized prior to study initiation.

Monitoring will be performed according to ICH GCP including but not limited to regular visits during the clinical study and a closeout visit. Data will be evaluated for compliance with the protocol and accuracy in relation to source documents. Following written standard operating procedures, the monitors will verify that the clinical study is conducted and data are generated, documented and reported in compliance with the protocol, GCP and the applicable regulatory requirements.

13.2.2 Implementing monitoring and audits at study sites

Monitors will participate in all key, planned activities, collaborating with implementation of the study. They will therefore comply with all the planned monitoring visits.

The monitoring plan will detail the frequency of monitoring visits and audits at the study site. The Study Monitoring Plan will cover instructions for monitoring the main aspects of the implementation of the study, including at least:

- Study authorizations and approvals and communication with the ethics committees
- Duties and Responsibilities of the Investigator/Institution
- Suitable resources
- Medical care for the participants
- Clinical Study compliance with the agreed protocol
- Laboratory aspects
- Informed consent of participants
- Data management, records and reports
- Stopping rules, early termination, or suspension of the study
- Sponsor's Responsibilities
- Responsibilities of the Monitors
- Auditor's Responsibilities

13.2.3 Training to ensure quality of the study

Study staff will receive specific training focused on the activities they will be performing. Specific training will be conducted prior to the cross-sectional surveys, mass campaign and interviews. The objective of this training program is to ensure that investigators are well prepared and trained, and understand the details and design of the study prior to implementation of the study.

GCP training or GCP refresher training will be provided to pre-identified staff.

13.3 Data Safety Monitoring Board

The remit and functions of the DSMB will be described in the DSMB Charter.

The aim of this committee is to protect the safety of trial participants while maintaining the study's scientific goals according to the protocol and in accordance with international and local standards. A first DSMB meeting will be convened before the study commences and the DSMB Charter and Terms of Reference will be set at this first meeting. Thereafter, DSMB meetings will be conducted every 3 months.

13.4 Inspections

The investigators and institutions involved in the study will ensure that regulatory authorities may conduct monitoring and auditing and inspection of the study implementation. This includes official reviews of documents, facilities, records, and any other resources that are deemed by the authorities to be related to the study and that may be located at the study site or the Sponsor's and/or contract research organization's facilities, or at other establishments deemed appropriate by the regulatory authority.

13.5 Completion or termination of the study

Upon completion of the study, a summary of the study's outcome and any required reports, if relevant, will be provided to the ERBs where required, and any reports will be provided to the regulatory authorities if applicable.

After completion or termination of the study all documents, summaries, and reports for ERBs or the regulatory authorities should be kept in the investigator site file (ISF).

13.6 Publication policy and final report

Timely reports of progress will be made available to MOH and health officials and other stakeholders, including communities.

A final report of the study will be prepared and shared with relevant partners as described above. The project will publish overall results in international peer-reviewed scientific journals and in relevant national journals and media. The results of the cluster randomized trial will be reported following the CONSORT extension for cluster-randomized trials.³

³ <http://www.consort-statement.org/extensions/overview/cluster-trials>

14 Study Organization

14.1 Study Team

A field study team will consist of nurses, communication officers, laboratory personnel, data management personnel, monitors, administrator and logistician. The field study team in Niger will be overseen by the Site Principal Investigator. He will be supported by a Project Coordinator, who will be responsible for maintaining communications between the field and office study teams.

The field team will be supported by a clinical study and project administration team located in Paris.

The qualitative component of this project will have their own dedicated team and will be led by qualitative researchers from the Université Abdou Moumouni.

14.2 Trial Steering Committee

A Trial Steering Committee (TSC) will be put in place, with members comprised of a relevant mix of people with experience in pneumococcal disease prevention and epidemiology, as well as knowledge in data management, ethics, and knowledge of the local community.

The overall task of the committee is to provide guidance and independent expertise on study design and conduct and ensure proper execution of the study. The Committee will meet prior to study initiation and at regular intervals thereafter to review study progress, consider recommendations of the DSMB and relevant ethics committees, and to agree on communications regarding the study.

1.1 Statistical Analysis Plan

A statistical analysis plan (SAP) is a comprehensive and detailed description of the methods for data analyses to be used in a clinical trial. A clear, detailed SAP will avoid post hoc decisions that may affect the interpretation of the data. This SAP includes details on the procedures for creating Tables, Listings, and Graphs from the results of a Phase IV study, which will be carried out to determine whether mass campaigns with fractional dose PCV10 would accelerate herd protection against pneumococcal transmission in Sub-Saharan Africa.

This is a separate document from statistical section of the protocol. Any changes in the statistical methods presented in the protocol and any additional statistical analysis not included in the protocol will be explained in this detailed statistical analysis plan of the study. This SAP includes a statement of the objectives of the trial, as stated in the protocol; identifies all primary and secondary end-points; specifies the hypotheses to be tested and any parameters that are to be estimated, in order to meet the trial objectives; defines the analysis populations to be used; and provides a full and detailed description of the methods of analysis including details of handling of missing data, dropouts, derived variables, etc.

1.2 Rationale

Pneumococcal vaccination campaigns targeting children up to 5 years of age with a full three-dose primary series have been shown to have an effect in the reduction of VT carriage and disease. However, in crises or settings with high prevalence of malnutrition, the high pneumococcal carriage prevalence is likely to extend to older age groups. Therefore, a single dose vaccination of a larger age group might be needed to control VT circulation. Currently, for Gavi-supported countries, such as Niger, PCV13 vaccine has a cost of US\$3 per dose. Pneumosil®, a PCV10 manufactured by Serum Institute of India Ltd, has the lowest price at US\$2 per dose of all WHO prequalified vaccines.

Even at the lower price point, mass campaigns targeting larger age groups would require many doses and might not be sustainable over time.

Mass campaigns using fractional doses of PCV could be a solution to overcome the high PCV costs, increase vaccine access and expand vaccination benefits through alternative strategies.

2. Study Objectives

2.1 Primary Objective

The primary objective is to evaluate whether a mass vaccination campaign targeting children approximately 1-9 years of age with a full dose of PCV is superior to the absence of vaccine in reduction of VT carriage prevalence at 6 months post-campaign, and subsequently to evaluate if a single 20% dose of PCV is non-inferior to a full dose.

2.2 Secondary Objectives

Analysis of the following secondary objectives will be described in this SAP:

- To measure the age-stratified prevalence of NP carriage of *S. pneumoniae* in children 1-9 years of age in the study area.

- To determine the effect of a mass vaccination campaign with one full dose of PCV in children 1 to 9 years of age on VT pneumococci carriage 6 months after vaccination
- To assess the occurrence of adverse events (AE) during 7 days and serious adverse events (SAE) during 28 days after administration of fractional and full doses of PCV.

The analyses of the two following secondary objectives will be described elsewhere:

- To model the potential effect of fractional dose PCV campaigns in other contexts using the results of the clinical trial.
- In the setting of a qualitative study, to develop recommendations on how a potential future fractional dose PCV mass campaign could be successfully planned, communicated, delivered and integrated into national immunization programmes using qualitative analysis.

3. Study Design and Assessment

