Although a relatively low cost PCV (Pneumosil®) is currently available, mass campaigns targeting large age groups with a full dose of vaccine would require a large quantity of vaccine and might not be sustainable over time. Fractional dosing of licensed vaccines have been considered for situations of high vaccine costs and/or supply chain shortages (22). Fractional doses administered through the intradermal route have been assessed for several vaccines including influenza, rabies, hepatitis B, inactivated polio vaccine (IPV) (23) and through the standard subcutaneous route for yellow fever vaccine (24). Following available evidence, fractional doses of IPV, rabies and yellow fever vaccines are recommended by WHO and used routinely in several countries and for outbreak response (25,26). Data from the original dose-finding studies for a pentavalent PCV indicate that a dose as low as 1/4th of the current dose in PCV10 could elicit adequate immunogenicity (27). A non-inferiority trial of fractional doses of PCV10 and PCV13 is currently underway in Kenya (ClinicalTrials.gov Identifier: NCT03489018; PI [name]). Following this, fractional doses of PCV could be a solution to overcome the high PCV costs, increase vaccine access and expand vaccination benefits through alternative strategies.

This study aims to assess the impact of a mass campaign with a single, fractional dose of Pneumosil®, a PCV10, on VT carriage. A 20% fractional dose (1/5th) will be used as a practical formulation to prepare and administer. This study will assess whether the impact of a single fractional dose mass campaign on carriage is non-inferior to a single full dose mass campaign in a cluster randomized trial in a low coverage setting in Niger. The results would provide evidence of the population-level direct and indirect impact of fractional dose in older children which will be completed by mathematical modelling, to inform the policy debate regarding PCV dosing schedules in different contexts. This trial and the modelling exercises that follow, would allow for larger scale evaluation of fractional dose PCV strategies in multiple contexts.

² Administrative coverage from UNICEF Immunization data <https://data.unicef.org/topic/child-health/immunization/>
Actual coverage from MSF-Epicentre data.

6 Study Objectives

Primary objective

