3.1.2 Sample Size and Power Considerations

The sample size has been calculated to respond to the objective of determining whether community level prevalence of VT pneumococci after a fractional dose PCV mass campaign among children aged 1-9 years is non-

Determining whether mass campaigns with fractional dose PCV10 would accelerate herd protection against pneumococcal transmission in Sub-Saharan Africa

inferior to that seen after a mass campaign among children aged 1-9 years using full dose PCV as well as determining the superiority of a full dose PCV mass campaign compared to no vaccination. Based on NP carriage studies conducted in Sub-Saharan Africa settings and considering an estimated coverage of 3 doses of PCV in children < 12 months of age of 48% in the study area, we estimate the prevalence of VT carriage, among 1-9 year old, to be between 25 and 35% and take the middle value, 30%, as an initial estimate. We assume a 50% reduction in PCV10 VT carriage after vaccination with a full dose and consider the prevalence of VT carriage amongst vaccinated children with a full dose 6 months after the vaccination campaign to be 15%.

Based on information from a study conducted in the area, we consider an intra-cluster correlation coefficient of 0.02. To test the non-inferiority of a mass campaign using fractional doses compared to a mass campaign using full doses, we have chosen a non-inferiority margin of 7.5% to ensure that a campaign with fractional doses provide at least half of the benefits provided by a campaign using full doses. We consider a 2.5% level of significance for a one-sided test and 90% power. With these assumptions, 27 clusters with 36 households sampled per cluster would provide a power of at least 90% (1944 individuals, with 972 in the full dose and 972 in the fractional dose arm). Non-inferiority will be achieved if the lower limit of the 95% confidence interval (CI) around the difference in the proportion of children with VT carriage (full dose group – fractional dose group) is $> -7.5\%$.

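### The second secondary objective repeats the full-dose half of the primary objective, while no carriage analysis compares the fractional-dose campaign with no campaign

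*Combined protocol and SAP*

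**What the plan says.** The primary objective (SAP 2.1, protocol section 6) has two steps. The first is whether the full-dose campaign "is superior to the absence of vaccine in reduction of VT carriage prevalence at 6 months post-campaign". The second is "subsequently to evaluate if a single 20% dose of PCV is non-inferior to a full dose".

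The second secondary objective (SAP 2.2, protocol section 6 and the protocol synopsis) is "To determine the effect of a mass vaccination campaign with one full dose of PCV in children 1 to 9 years of age" on VT carriage at 6 months. It names no comparator.

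The rationale (protocol section 5) states: "This study aims to assess the impact of a mass campaign with a single, fractional dose of Pneumosil®, a PCV10, on VT carriage". It then says that the study will assess "whether the impact of a single fractional dose mass campaign on carriage is non-inferior to a single full dose mass campaign".

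The between-arm carriage contrasts in protocol 6.1 and 12 and in SAP 4.3 and 4.3.2.1 are full dose v control (superiority), then fractional v full dose (non-inferiority, margin 7.5 points), the second tested only if the first succeeds. The seasonality sensitivity analysis in SAP 4.3.2.1 is also full dose v control. For safety, protocol section 12 and SAP 4.3.3 compare each vaccine arm with control.

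SAP 3.1.2 justifies the margin as chosen "to ensure that a campaign with fractional doses provide at least half of the benefits provided by a campaign using full doses".

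**The concern.** The secondary objective has the same arm, outcome and time point as the first half of the primary objective, so it adds no question. It also has no analysis of its own: the secondary outcome in SAP 3.2.1.2 is non-VT carriage, and the methods text describes no further VT contrast. (The heading for secondary analysis at the end of SAP 4.3.2.1 has no text in the copy available. I take it that nothing was lost there.)

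Meanwhile the question a programme deciding on fractional doses would ask, how much carriage falls compared with doing nothing, gets no estimate with a clustering-adjusted interval. The answer has to be pieced together from full-dose superiority and the non-inferiority margin. That chain is only as strong as the assumed 15-point full-dose effect. It also gives nothing if non-inferiority fails, even if the fractional campaign worked.

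**Working it through.** **Inputs** (SAP 3.1.2 and 3.1.3): control carriage 30%, full-dose carriage 15%, ICC 0.02, margin 7.5 points, 27/27/9 clusters, 36 children per cluster. All 36 are taken as swabbed, and the comparison is of post-campaign prevalence.

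**1. The plan's own figures reproduce.**
- Design effect at 36 per cluster: 1 + 35 × 0.02 = 1.70. Effective sizes: 9 × 36/1.70 = 190.6 (control) and 27 × 36/1.70 = 571.8 (each vaccine arm).
- Non-inferiority: n = (1.960 + 1.282)² × 2 × 0.15 × 0.85/0.075², about 477 per arm. 477 × 1.70/36 = 22.5 clusters. With 27 clusters, power is 94%, or 90% with the variance taken at the margin. This agrees with the stated minimum of 90%.
- Superiority: 161 per arm before clustering. Design effect at 30 per cluster is 1.58, and 161 × 1.58/30 = 8.5, rounded up to 9 clusters as stated.

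**2. What the margin secures.** For a true full-dose effect E, the smallest fractional effect compatible with the margin is E − 7.5, a share (E − 7.5)/E. This reaches one half only when E is at least 15 points. At E = 9 it is 1.5/9 = 17%.

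**3. What superiority requires.** At observed carriage of 30% v 22%, SE = √(0.21/190.6 + 0.1716/571.8) = 3.74 points. Significance needs 1.96 × 3.74 = 7.3 points, or 7.6 points with t on 34 df. The first test can therefore be passed at about half the effect on which the margin was based.

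**4. A result that passes both tests.** Observed carriage 30% control, 21% full, 23.5% fractional:

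| Contrast | Difference | SE | 95% CI | Result |
|---|---|---|---|---|
| Control − full | 9.0 | 3.73 | lower limit +1.7 | superiority met |
| Full − fractional | −2.5 | 2.46 | lower limit −7.3 | non-inferiority met |
| Control − fractional | 6.5 | 3.76 | −0.9 to 13.9 | no effect not excluded |

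With t-based limits (34, 52 and 34 df) the lower limits are +1.4, −7.4 and −1.1, so the three conclusions are unchanged.

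**5. The converse.** Observed carriage 30% control, 15% full, 20% fractional. Full − fractional is −5.0 with SE √((0.1275 + 0.16)/571.8) = 2.24, so the lower limit is −9.4 and non-inferiority fails. Control − fractional is 10.0 with SE 3.72, so the 95% CI is 2.7 to 17.3. If these are the true values, non-inferiority fails while fractional v control is significant in about 59% of trials (normal-approximation simulation).

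**6. Precision of the missing contrast.**
- At 15% fractional carriage: SE 3.64 points, CI half-width 7.1, power 98% to 99%.
- At 22.5%: SE 3.75 points, half-width 7.4, power 49% (t), 52% (unpooled normal) or 55% (pooled normal).

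**The case against.** **The documents never promise this contrast.** The rationale names no comparator for impact, and goes on to frame the question as non-inferiority to the full dose. This stands. A reader might infer that the plan contradicts its own stated aim. It does not: fractional v control is a fair reading of what measuring impact needs, but the documents do not state it as an objective.

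**Some comparison with control exists.** This stands for safety, so only the carriage contrast is missing. Carriage prevalence will also be shown for all three arms with 95% CIs. That is useful, but separate arm prevalences do not give a clustering-adjusted difference or its interval.

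**The superiority gate protects against an ineffective comparator.** Largely true. A reader might infer from steps 2 and 3 that both tests can readily be passed while the fractional campaign keeps almost none of the effect. That ignores the non-inferiority interval. At an observed full-dose effect of 7.5 points (22.5% carriage), non-inferiority requires observed fractional carriage of at most about 25.1%. The observed fractional effect is then at least 4.9 points, about 66% of the full-dose effect. With a true full-dose effect of 7.5 points and a true fractional effect of zero, both tests pass only about 0.6% of the time.

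**Another contrast does not repair the margin.** Correct. It shows the reader what the margin leaves open.

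**Conclusion.** The duplication is plain from the text, and no carriage analysis compares fractional dose with control. No planned primary conclusion is invalid because of it. The cost is in interpretation: the trial could declare non-inferiority while its own randomised data do not exclude no effect against no campaign, or fail non-inferiority without reporting a clear benefit over no campaign. The first case matters mainly if the full-dose effect falls short of 15 points. The second can arise even when the full-dose assumption is right.

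The figures rest on post-campaign prevalence, ICC 0.02 and 36 swabs per cluster. Two departures matter:
- **Fewer swabs.** If the 20% refusal or absence left 28.8 children per cluster, the design effect is 1.556 and the SE at 15% v 30% rises to 3.9 points. Power at a 15-point effect is then about 96% to 98%.
- **Change from baseline** (the endpoint in SAP 4.1). Treating the two surveys as independent, SE = √(0.21/190.6 + 0.1275/571.8 + 0.21/190.6 + 0.21/571.8) = 5.3 points and power at 15 points is 81%. Significance then needs about 1.96 × 5.3 = 10.4 points, still below 15.

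**What to change.** In protocol section 6 and SAP 2.2, replace the duplicate objective with the effect of one fractional (1/5) dose campaign v no campaign on VT carriage at 6 months.

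In SAP 4.3.2, add the risk difference with 95% CI for fractional dose v control, from the same GEE approach as the primary contrasts. Report it beside the non-inferiority result whether or not non-inferiority is met, as a secondary estimate outside the confirmatory sequence. If a formal claim is wanted, the test can be placed third in the sequence. The estimate itself should not depend on passing non-inferiority, because that would withhold it in the situation of step 5.

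In the same edit, correct the sentence in SAP 4.3.2.1 that gives the fractional dose as comparator for the superiority model, since the paragraph before it names the control arm.

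The cost is one objective line and one model contrast on data already collected. The two primary tests keep their full alpha. The drawback is limited precision: a CI half-width of about 7 points, and only about 50% to 55% power at a 7.5-point effect. The contrast should therefore be read as an estimate, and a non-significant result should not be taken as evidence of no effect.

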3.1 Study Design

This is a Phase IV, 3-arm, observer-blinded, cluster-randomized controlled trial, implemented in rural villages of the Madarounfa District of Niger.

3.1.1 Study cohorts

Clusters will be randomized to full dose mass vaccination campaigns, fractional dose mass vaccination campaigns or the control arm in 3:3:1 allocation ratio. Clusters will be composed of a village or group of closely-neighbouring villages that share a school or market, and will be limited to a population of between 500 and 4000 persons. Stratified randomization will be used to account for proximity to the nearest health centre (<5 km vs ≥5 km). In the event of significant imbalance in carriage of VT pneumococci between clusters in the baseline survey, randomization may also be stratified by baseline prevalence upon the decision of the Trial Steering Committee. For this reason, randomization will happen after the results of the baseline survey are known.

Vaccination will target all children aged 1 to 9 years of age residing in the selected villages. (If baseline survey data unexpectedly shows very low prevalence of carriage at the extremes of this age range, the target age group may be adjusted upon recommendation of the trial steering committee.) We estimate that children eligible for the vaccination campaigns will represent 30% of the total population. With an estimated average of 2000 people per cluster, vaccination will target approximately 600 children 1-9 years of age in each cluster receiving vaccine. In total, in the 54 clusters receiving vaccine, the mass vaccination campaign with single full- or fractional-dose PCV is expected to target approximately 32,400 children 1-9 years of age.

Prior to the mass vaccination campaign, a cross-sectional survey will be implemented to estimate community-level carriage of VT pneumococci, as well as to collect data on household composition, social interactions and PCV vaccination coverage in the routine EPI. A total of 36 households in each cluster will be invited to participate in the cross-sectional survey. For the purposes of this study, a household is defined as a group of people living under the authority of a head of household, sleeping under the same roof, and sharing at least one meal per day, for at least two weeks, independent of any family ties. Selection of households will be based on probability sampling. The required number of households in each cluster will be randomly selected using simple random sampling based on an exhaustive list of heads of household in the cluster.

Six months after the mass vaccination campaign, the post- vaccination cross-sectional survey will be implemented. This will be used to estimate community level carriage of VT pneumococcus after a single-dose PCV delivered as full or fractional dose as well as carriage in the clusters that received no vaccination. The survey

Determining whether mass campaigns with fractional dose PCV10 would accelerate herd protection against pneumococcal transmission in Sub-Saharan Africa

will target the same number of children as the baseline survey and will follow the same methodology with the households selected by simple random sampling from the sampling frame.

Sampling will be independent between the two surveys.

